### 3.2 Exclusion Criteria

Patients must NOT meet any of the following exclusion criteria

- 3.2.1 Received an investigational agent within 4 weeks prior to enrollment (see section 5.3.12).
- 3.2.2 Stage T4 prostate cancer by clinical examination or radiologic evaluation.
- 3.2.3 Hypogonadism or severe androgen deficiency as defined by screening serum testosterone less than 50 ng/dL below the normal range for the institution.
- 3.2.4 Prior androgen deprivation, chemotherapy, surgery, or radiation for prostate cancer.
- 3.2.5 Receiving concurrent androgens, anti-androgens, estrogens, or progestational agents, or received any of these agents within the 6 months prior to enrollment or having taken finasteride or dutasteride within 30 days of registration.
- 3.2.6 History of another active malignancy within the previous 5 years other than curatively treated nonmelanomatous skin cancer and superficial bladder cancer. Participants treated for malignancy with no relapse within two years are eligible to participate in the study.
- 3.2.7 Uncontrolled intercurrent illness including, but not limited to, ongoing or active infection.
- 3.2.8 Severe concurrent disease, infection, or co-morbidity that, in the judgment of the Investigator, would make the patient inappropriate for enrollment.
- 3.2.9 Unwilling to use contraceptives while on study if relevant to patient.
- 3.2.10 History of seizure or any condition or concurrent medication that may predispose to seizure.
- 3.2.11 History of loss of consciousness or transient ischemic attack within 12 months prior to enrollment.
- 3.2.12 Clinically significant cardiovascular disease, including:
  - Myocardial infarction within 3 months of enrollment;
  - Uncontrolled angina within 3 months of enrollment;
  - Congestive heart failure New York Heart Association (NYHA) class 3 or 4, or history of congestive heart failure NYHA class 3 or 4 in the past, unless a screening echocardiogram or multi-gated acquisition scan performed within 3 months results in a left ventricular ejection fraction  $\geq 45\%$ ;
  - History of clinically significant ventricular arrhythmias (e.g., ventricular tachycardia, ventricular fibrillation, torsades de pointes);
  - History of Mobitz II second degree or third degree heart block without a permanent pacemaker in place;
  - Hypotension as indicated by systolic blood pressure  $< 86$  mmHg on 2 consecutive measurements at the Screening visit;
  - Bradycardia as indicated by a heart rate  $< 50$  beats per minute at the Screening visit;
  - Uncontrolled hypertension as indicated by systolic blood pressure  $> 170$  mmHg or diastolic blood pressure  $> 105$  mmHg on 2 consecutive measurements at the screening visit;
  - EKG demonstrating equal to or greater than grade III toxicity according the

CONFIDENTIAL

This document is confidential. Do not disclose or use except as authorized.

Version 13.0 Protocol Version Date: 1/09/2015

NCI Common Terminology Criteria for Adverse Events (CTCAE) version 4.0

- 3.2.13 History of gastrointestinal disorders (medical disorders or extensive surgery) that may interfere with the absorption of oral study drug(s) within 3 months of enrollment.
- 3.2.14 Major surgery within 4 weeks of registration.
- 3.2.15 Previous use, or participation in a clinical trial, of an investigational agent that blocks androgen synthesis (e.g., abiraterone acetate, TAK-700, TAK-683, TAK-448) or targets the androgen receptor (e.g., enzalutamide, BMS 641988); ketoconazole.
- 3.2.16 Any condition or reason that, in the opinion of the Investigator, interferes with the ability of the patient to participate in the trial, places the patient at undue risk, or complicates the interpretation of safety data.
- 3.2.17 Need for any of the medications on the list of drugs to be used with caution or to be avoided (see APPENDIX F).
- 3.2.18 Use of herbal or alternative remedies that may affect hormonal status such as Prostasol or PC-SPES.

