Fatigue was the most frequently reported adverse event, with dose-dependent increases of Grade 3 fatigue (0% at 150 mg/day, 9% at 240 mg/day, 15% at 360 mg/day, and 20% at 480 mg/day). The dose of 240 mg/day was defined as the maximum tolerated dose. At doses of 240 mg and above, an increasing proportion of patients needed dose reductions for fatigue. Dose reductions were needed in 1 of 29 patients (3%) that received 240 mg/day, 3 of 28 patients (11%) that received 360 mg/day, and 5 of 22 patients (23%) that received 480 mg/day, and 0 of 58 patients that received 30, 60, or 150 mg/day. After dose reductions, the symptoms resolved. Only 1 patient discontinued treatment due to fatigue with an onset coinciding with prostate specific antigen (PSA) rise. Overall, the most common mild (grade 2) adverse events were fatigue ( $n = 38$  [27.1%]), nausea ( $n = 12$  [8.6%]), dyspnea ( $n = 11$  [7.9%]), anorexia ( $n = 8$  [5.7%]), and back pain ( $n = 8$  [5.7%]). Fatigue, nausea, and anorexia were the only mild adverse events with an increasing incidence as the dose of enzalutamide was increased. None of the grade 2 events required dose modification or the discontinuation of treatment, apart from 1 patient treated at 480 mg/day who had nausea at baseline and stopped therapy after 7 weeks.

CONFIDENTIAL

This document is confidential. Do not disclose or use except as authorized.

Version 13.0 Protocol Version Date: 1/09/2015

In the randomized clinical trial, 7 of 800 (0.9%) patients treated with enzalutamide 160 mg once daily experienced a seizure. No seizures occurred in patients treated with placebo. Seizures occurred from 31 to 603 days after initiation of enzalutamide. Patients experiencing seizure were permanently discontinued from therapy and all seizures resolved. There is no clinical trial experience re-administering enzalutamide to patients who experienced seizures.

The safety of enzalutamide in patients with predisposing factors for seizure is not known because these patients were excluded from the trial. These exclusion criteria included a history of seizure, underlying brain injury with loss of consciousness, transient ischemic attack within the past 12 months, cerebral vascular accident, brain metastases, brain arteriovenous malformation or the use of concomitant medications that may lower the seizure threshold.

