### **3. PARTICIPANT SELECTION**

Participants must meet the following criteria on screening examination to be eligible to participate in the study:

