## 5.3 General Concomitant Medication and Supportive Care Guidelines

### 5.3.1 Prior and Concomitant Therapy

**5.3.1.1** Medications taken within 14 days prior to the first dose of study drug will be documented on the appropriate case report form as a prior medication. Medications taken after the first dose of study medication and until 30 days following the last dose of any study drug (enzalutamide) will be documented on the appropriate case report form as concomitant medication. All concomitant medication(s) must be reported on the appropriate case report form. Prior and concomitant medications include all vitamins, herbal remedies, over the counter, and prescription medications. If an intermittent or as needed use of any medication during the study is due to an adverse event, then the adverse event must also be recorded on the adverse event case report form.

**5.3.1.2** The following medications are prohibited within 4 weeks of first study drug administration and throughout time on study, unless otherwise indicated below:

Androgens (e.g., testosterone, dihydroepiandrosterone), estrogens, or progestational agents Ketoconazole, diethylstilbestrol, PC-SPES, and other preparations such as saw palmetto thought to have endocrine effects on prostate cancer:

- Radiopharmaceuticals such as strontium (89Sr) or samarium (153Sm), radium 223 ○ Aldactone, Spironol (spironolactone), eplerenone;
- Herbal medications, such as Prostasol and PC-SPES, St. Jon's Wort; ○ Cancer Vaccine therapy;
- Non-cytotoxic, non-investigational anti-tumor treatment;
- Use of an investigational agent, unless prior approval by the PI, [name], for a shorter washout period, provided the patient has adequately recovered from any ongoing adverse events.
- Any alternative remedy that may affect hormonal status.

CONFIDENTIAL

This document is confidential. Do not disclose or use except as authorized.

Version 13.0 Protocol Version Date: 1/09/2015

- Caution is advised for patients taking drugs metabolized through either CYP3A4 or CYP2C8 pathways. Please see Appendix F.

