**Appendix F:**

Drugs to avoid because of interaction with CYP2C8 or CYP3A4 metabolic pathways

Gemfibrizil, carbamazepine, phenobarbital, pentobarbital, phenytoin, rifabutin, rifampin, rifapentine, nafcillin, modafinil, etavirenz, efavirenz, bosentan, cyclosporin, ergotamine, quinidine, sirolimus, tacrolimus, alfentanil, pimozide, St. John's Wort, ketoconazole, sertraline, digitoxin, haloperidol, ketamine, doxycycline, isoniazid, etravirine, dihydroergotamine and fentanyl.

Drugs to be used with caution

Warfarin (will likely require a change in warfarin dosing), omeprazole, midazolam, ciprofloxacin.

CONFIDENTIAL

This document is confidential. Do not disclose or use except as authorized

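### Medication that may predispose to seizure bars entry under 3.2.10, but nothing in the plan restricts starting such a drug during enzalutamide treatment

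*Combined protocol and SAP*

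**What the plan says.** Section 3 introduces its criteria with "Participants must meet the following criteria on screening examination to be eligible to participate in the study". Among the exclusions, 3.2.10 lists "History of seizure or any condition or concurrent medication that may predispose to seizure".

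The reason is in 2.1.1. In the randomized trial cited there, 7 of 800 men (0.9%) on 160 mg daily had a seizure and none on placebo did. Onset ran from day 31 to day 603. The section continues: "The safety of enzalutamide in patients with predisposing factors for seizure is not known because these patients were excluded from the trial". Its list of those exclusions includes "the use of concomitant medications that may lower the seizure threshold".

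Drugs during the study are governed by 5.3.1:

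- 5.3.1.1 requires recording: "All concomitant medication(s) must be reported on the appropriate case report form". The recording period ends 30 days after the last enzalutamide dose.
- 5.3.1.2 opens its list with "The following medications are prohibited within 4 weeks of first study drug administration and throughout time on study, unless otherwise indicated below". The list ends with "Caution is advised for patients taking drugs metabolized through either CYP3A4 or CYP2C8 pathways" and a pointer to Appendix F.
- Appendix F heads its first list "Drugs to avoid because of interaction with CYP2C8 or CYP3A4 metabolic pathways" and adds four drugs to be used with caution.

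New drugs during treatment are foreseen. For toxicity of grade 3 or higher, 6.2.2.3 asks sites to consider prophylactic medication where appropriate, and to adjust or add medication if the toxicity recurs. Section 6.3 asks for appropriate medical treatment of toxicity and gives antiemetics and anti-diarrheals as examples.

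**The concern.** The pharmacological reason for 3.2.10 is the same on day 40 as at screening: the man is exposed to a drug with a recognised seizure risk, and the added medication may predispose him further. If the restriction works only at entry, the plan protects him from a drug he already takes but not from the same drug started a month later. A site or an outside prescriber could start it without breaching the protocol, and no rule would prompt the site to look for an alternative or to ask the medical monitor first. What is at stake is participant safety during treatment, not the primary analysis.

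**Working it through.** There is no plan figure to reproduce for the gap itself. The check is to take each provision that could restrict such a drug after day 1 and ask whether it does.

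| Provision | When it applies | What it covers | Restricts starting a drug that may predispose to seizure? |
|---|---|---|---|
| 3.2.10 | Screening | Seizure history, conditions, concurrent medication | At entry only |
| 3.2.17 | Screening | Need for an Appendix F drug | At entry, and only for listed drugs |
| 5.2.1 | On treatment | Other agents given to treat the malignancy | No |
| 5.2.2, cycle-start criteria | Each cycle | Blood counts, liver enzymes, resolution of severe adverse events | No |
| 5.3.1.1 | To 30 days after last dose | Recording of all medication | No, recording only |
| 5.3.1.2 | 4 weeks before first dose and on study | Hormonal and endocrine-active agents, radiopharmaceuticals, spironolactone and eplerenone, certain herbals, vaccines, other anti-tumor or investigational treatment; CYP caution | No |
| 2.1 and Appendix F | On treatment | Drugs listed for CYP interaction | Not as a class |
| 6.2 | On treatment | Toxicity management; the only drug treatment barred is of the tamoxifen type, for gynecomastia | No |
| 6.1.3 and 6.3, seizure text | After a seizure | Stop enzalutamide, remove from study | No, acts after the event |

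Appendix F has 31 drugs to avoid and 4 to use with caution, 31 + 4 = 35 entries. The first list gives CYP interaction as its ground, and 2.1 discusses these drugs in CYP terms. Some entries may also affect seizure threshold. The documents do not say which, so the count describes the stated ground and does not measure coverage or harm.

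The medical monitor's role has limits. Under 5.2.2 the monitor hears of adverse events that lead to holding, stopping or changing the dose. Under 6.2.2.3 the monitor approves the resumption at 120 mg. Neither requires notice of which drug was added, or of a drug started without a hold.

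Period of exposure: 6 cycles × 28 days = 168 days, for up to 71 enrolled men. The earliest seizure in 2.1.1, day 31, falls inside that course.

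How long a restriction should outlast the last dose: 2.1.1 gives a single-dose terminal half-life of about 6 days (range 3 to 10).

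- Five half-lives at 6 days: 5 × 6 = 30 days, leaving 0.5^5 = 3.1% of the parent drug.
- Over the range: 5 × 3 = 15 days to 5 × 10 = 50 days. With a 10-day half-life, 30 days is three half-lives, leaving 0.5^3 = 12.5%.

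Thirty days is therefore a reasonable middle value and matches the recording period in 5.3.1.1. It rests on the parent drug; the documents give no half-life for the active metabolite.

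**The case against.** **The word concurrent in 3.2.10 could be read as continuing on study.** It stands under criteria to be met at screening, and no on-study section refers back to it.

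**The advice may sit elsewhere.** The Investigator's Brochure, package insert and consent form are not in the documents, and advice to participants about new medicines would often be in the consent form. This stands as a caveat. If those sources already give the advice, the amendment only brings it into the protocol.

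**Other controls exist.** Section 5.4.3 lets the investigator end treatment when a man's condition changes. Section 5.3.1.1 requires the adverse event behind an as-needed drug to be recorded, and 10.4.2 sends non-serious events to the overall principal investigator. Radiotherapy brings frequent attendance: 75.6/1.8 = 42 to 79.2/1.8 = 44 fractions. All of this lowers the concern. But the first is discretionary, the reporting comes after the fact, and radiotherapy visits are not medication reviews.

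**Section 2.1 is firmer than the caution in 5.3.1.2.** It says several groups of interacting drugs should be avoided, and cites Appendix F for some of them. That is correct, but the ground is still CYP interaction.

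Three stronger readings are tempting, and the documents do not support them.

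- A reader might infer that the supportive drugs the protocol names, such as antiemetics, themselves predispose to seizure. No section says so. The point is only that new drugs are foreseen and the class is not restricted.
- A reader might take a harm rate from 2.1.1. At 7/800 = 0.875%, the chance of at least one seizure among 71 men is 1 − (1 − 0.00875)^71 = 46.4%. That is not the effect of this gap. It carries over a rate from men with advanced disease, some with onset far beyond 168 days, and from a trial that excluded men with predisposing factors.
- A reader might infer that the plan carries every other excluded drug into 5.3.1.2 and missed only this one. It does not: anti-androgens, finasteride and dutasteride, excluded under 3.2.5, are not named there either.

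**Conclusion.** The gap is real and modest. A class of drugs excluded at entry on safety grounds has no matching restriction during treatment, although the protocol itself says safety with such drugs is not known. This is more than missing detail, because a site that follows the plan exactly can still start such a drug.

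The size cannot be put as a harm rate, and none is claimed. What can be said is that the class is unrestricted for 168 days of treatment. The decision rule of 44 or more successes among 64 evaluable men, with its stated error rates of 0.095 and 0.099, does not depend on this point.

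The conclusion assumes that 3.2.10 binds at screening only, as section 3 is worded, and that no document outside the protocol already imposes the restriction on sites. The change is worth making because it costs little.

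**What to change.** Add a bullet to 5.3.1.2:

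> *Medications that may predispose to seizure (as in 3.2.10) are to be avoided from the first dose of enzalutamide until about 30 days (about five half-lives) after the last dose, including drugs added under 6.2.2.3 or 6.3; use an alternative, and if none is suitable contact the medical monitor before the drug is started.*

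This keeps the scope of 3.2.10. A narrower wording, such as drugs known to lower the threshold, would leave some drugs that bar entry unrestricted on study.

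Two supporting changes:

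- Check the restriction at the existing 28-day medication reviews.
- Add a line to the Appendix H diary instructions telling participants to call the study team before starting any new medication. The calendar marks the last medication review, and collection of the diary, at the end of cycle 6. Participants should be told then that the instruction runs for a further 30 days or so.

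If example drugs are listed, put them under 5.3.1.2 or in a separate list in Appendix F. A list in Appendix F also feeds exclusion 3.2.17, but 3.2.10 already excludes these drugs at entry, so eligibility should not materially change.

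The cost is a protocol amendment and a check at visits already scheduled, on data already recorded under 5.3.1.1. The downside is that some men will need an alternative drug and sites will take some extra calls. The route through the medical monitor keeps necessary care available.

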### **3.3 Inclusion of Women, Minorities and Other Underrepresented Populations**

Women are not affected by prostate cancer and therefore are not eligible. Efforts will be made to enroll patients that are minorities. African Americans have a higher incidence of prostate cancer and effort will be made to recruit these men to this study.

## **4. REGISTRATION PROCEDURES**

### **4.1 General Guidelines for DF/HCC and DF/PCC Institutions**

Institutions will register eligible participants with the DF/HCC Quality Assurance Office for Clinical Trials (QACT) central registration system. Registration must occur prior to the initiation of therapy. Any participant not registered to the protocol before treatment begins will be considered ineligible and registration will be denied.

A member of the study team will confirm eligibility criteria and complete the protocol-specific eligibility checklist.

Following registration, participants may begin protocol treatment. Issues that would cause treatment delays should be discussed with the Principal Investigator. If a participant does not receive protocol therapy following registration, the participant's protocol status must be changed. Notify the QACT Registrar of participant status changes as soon as possible.

### **4.2 Registration Process for DF/HCC and DF/PCC Institutions**

The QACT registration staff is accessible on Monday through Friday, from 8:00 AM to 5:00 PM Eastern Standard Time. In emergency situations when a participant must begin

CONFIDENTIAL

This document is confidential. Do not disclose or use except as authorized.

Version 13.0 Protocol Version Date: 1/09/2015

treatment during off-hours or holidays, call the QACT registration line at [contact] and follow the instructions for registering participants after hours.

The registration procedures are as follows:

1. Obtain written informed consent from the participant prior to the performance of any study related procedures or assessments.
2. Complete the protocol-specific eligibility checklist using the eligibility assessment documented in the participant's medical/research record. **To be eligible for registration to the study, the participant must meet each inclusion and exclusion criteria listed on the eligibility checklist.**

**Reminder:** Confirm eligibility for ancillary studies at the same time as eligibility for the treatment study. Registration to both treatment and ancillary studies will not be completed if eligibility requirements are not met for all studies.

3. Fax the eligibility checklist(s) and all pages of the consent form(s) to the QACT at [contact].
4. The QACT Registrar will (a) validate eligibility, (b) register the participant on the study, and (c) enroll the participant when applicable.
5. The QACT Registrar will send an email confirmation of the registration and/or enrollment to the person initiating the registration immediately following the registration and/or enrollment.

## 5. TREATMENT PLAN

**5.1 Pretreatment criteria:** Patients with biopsy confirmed prostate cancer who meet eligibility criteria as defined in section 3.

### 5.2 Agent Administration

5.2.1 Treatment will be administered on an outpatient basis. Expected toxicities and potential risks as well as dose modifications for enzalutamide are described in Section 6 (Expected Toxicities and Dosing Delays/Dose Modification). No investigational or commercial agents or therapies other than those described below may be administered with the intent to treat the participant's malignancy.

CONFIDENTIAL

This document is confidential. Do not disclose or use except as authorized.

Version 13.0 Protocol Version Date: 1/09/2015

5.2.2 Patients will be treated in 6 (28 +/- 3 days) cycles. EBRT will be initiated 7-10 weeks into enzalutamide therapy. Patients will be seen every 28 (+/- 3 days) days for history and physical, adverse event and concomitant medication assessment. At these visits routine laboratory parameters will be obtained and a subset of these must be reviewed prior to dispensing the investigational agent. The routine laboratories at the beginning of each cycle should be completed per the Study Calendar in section 8.

The criteria to treat at the beginning of each cycle are:

- ANC greater than 1,000mm^3
- Hgb greater than 8.0 g/dL
- Platelets greater than or equal to 50,000
- ALT less than 3.5x upper limit normal
- AST less than 3.5x upper limit normal

Any grade (3 or greater) non-hematologic adverse event (such as fatigue, etc.) must be resolved to (grade 1 or less) in order to continue therapy. The Medical Monitor should be notified of any adverse events that require holding, stopping or dose modifications of study drug.

#### **5.2.2.1 Identity of Investigational Product**

The study drug, enzalutamide, has the chemical name 3-(4-cyano-3-trifluoromethylphenyl)-1-[3-fluoro-4-(methylcarbamoyl) phenyl]-5,5-dimethyl-2-thioxoimidazolin-4-one. The drug substance has no chiral centers and no salt forms are available at ~ pH 2 to 10. It is essentially insoluble in water, but partially soluble in lipid-based solutions.

Enzalutamide inhibits androgen receptor signaling with a novel mechanism. Enzalutamide binds to the androgen receptor and is inhibited from translocation into the nucleuse thereby blocking androgen receptor interaction with the chromatin and androgen inducible effects. Enzalutamide with LH-RH agonists have been shown to improve survival in castrate resistant prostate cancer (4). In an unpublished recently completed study, enzalutamide was shown to be safe in hormone-naïve prostate cancer patients with minimal toxicity. Effects on serum PSA levels and clinical outcome in this population are presently unavailable.\

